12. THEORETICAL FRAMEWORK

We are interested to assess whether earlier suture removal reduces stitch marks in wounds where close approximation of wound edges can be achieved with dermal sutures. In doing so we hope to provide evidence that earlier suture removal reduces the risk of suture marks without increasing wound complications.

As the incidence of suture marks is currently uncertain and the impact that these have on the patient is unknown we intend to perform a feasibility study prior to conducting a randomized controlled trial. This study would give an indication as to the sample size required to power our RCT correctly. It will also provide an indication as to the ease of recruitment, patient participation, loss to follow-up, and complication rate. Furthermore, it will allow us to evaluate the use of our chosen assessment tools.

We have designed a single centre, randomized, blinded, parallel group feasibility study to assess viability of a randomized control trial (RCT) to answer this question.

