14. AIMS AND OBJECTIVES

Aim:

To test the feasibility of conducting a definitive trial looking at outcomes for earlier removal of percutaneous sutures (7 days versus 10 days) for patients undergoing wide local excision and primary closure for treatment of skin cancers on the chest or back in dermatology.

Objectives:

1. To work out the standard deviation of the outcome measure (suture marks versus no suture marks) in order to estimate a sample size required for a properly powered RCT. (The incidence of 'suture marks' and the impact that these have on patients is currently unknown).
2. To provide some preliminary data on the incidence of wound complications and overall scar cosmesis in each group and ensure that this does not differ from expected:
 - a. *Overall cosmesis*
 - b. *Risk of post-operative bleeding*
 - c. *Risk of surgical site infection*
 - d. *Risk of wound dehiscence (opening up of scar)*
3. To assess the willingness of participants to be randomized.
4. To assess the willingness of clinicians to recruit patients.
5. To assess follow-up rates and adherence.
6. To assess the characteristics and ease of use of the proposed outcome measures including POSAS for scar assessment, a VAS, and patient reported outcome for complications including dehiscence and infection.
7. To gain feedback from patients at their three month follow up appointment on the patient pathway including the trial information leaflet and consent process.
8. To collect data on any additional costs that we may incur that have not been planned for, to inform costing for a future trial e.g. additional printing of PIS or consent forms or additional clinic booking slots
9. To use the gathered data to refine the design of the proposed RCT.

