16.4 Randomization and Blinding

Timing of Suture Removal to Reduce Scarring in Skin Surgery

Patients will be randomized into two groups following acceptance into the trial. A dermatology nurse, independent to the research trial and not involved in data collection or analysis, will use a random number generator to prepare 60 sealed envelopes, labelled 'participant 1' to 'participant 60'. These sealed envelopes will contain a slip of paper that either says 'suture removal at 7 days group' or 'suture removal at 10 days group'. During preparation of these envelopes using the random number generator, an odd number produced will be 'suture removal at 7 days group' and an even number will be 'suture removal at 10 days group'. The nurse who prepares these envelopes will be independent of the research trial to avoid any selection bias and maintain concealment. They will also have completed a 'Good Clinical Practice' (GCP) certificate. The surgeon and members of the research team involved in data gathering and analysis will be blinded to allocation.

After written consent to the trial has been gained, and excision of the lesion performed, the patient will leave the theatre room alongside one of our dermatology nurses/HCAs who is independent of the research team in order to maintain concealment and prevent selection bias. The patient and nurse/HCA will open one of the sealed envelopes, in numbered order, to reveal which arm of the trial they have been allocated to. The patient will be requested not to disclose which arm of the trial they were in. The theatre nurse or healthcare assistant will then discuss the post-operative wound care and timing of suture removal with the patient.

Patient blinding is not feasible as patients need to know which day to have their sutures removed post-surgery.

Before the patient leaves the department, an appointment will be booked with their GP for suture removal at either 7 or 10 days. If their GP does not have the capacity to remove the sutures on the given day, an appointment will be booked within the dermatology department on the given day for suture removal.

If the patient cannot attend the appointment for suture removal specifically on day 7 or 10, they will be removed from the study.

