The envelope containing the slip of paper with the randomized trial arm will be re-sealed and placed in a larger envelope labelled with the participant number. The signed consent form will also be kept in this labelled participant envelope, which will be placed in a secure location in line with data governance.

Concealment of the trial arm allocation will be maintained until trial completion. However, the code could be broken in the event of a significant adverse event.

All recorded data will be anonymized prior to statistical analysis by the statistician.

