17. DATA ANALYSIS METHODS

[name], Statistical advisor, Royal Devon and Exeter hospital has been consulted.

Data collection and input will be carried out by the research team who will be employed by the RDEFT and will comply with local and national information governance standards. A password-protected Excel spreadsheet will be set up on a Trust computer in the Dermatology Department - also password protected. All paper and electronic data will be collected and stored in compliance with data protection guidelines, good clinical practice in research guidance and Trust clinical governance policy.

A feasibility study will provide an opportunity to assess the data to be collected and the choice of appropriate statistical tests for a future definitive trial. Data analysis will involve statistical methods appropriate to the data collected. The statistical analysis for the feasibility study will be descriptive for each group as hypothesis testing is not an aim of the feasibility study and it is likely to be underpowered for that anyway. Descriptive statistics of baseline characteristics will be compared between study groups to demonstrate the effectiveness of randomisation. Continuous outcome

Timing of Suture Removal to Reduce Scarring in Skin Surgery

data will be tested for normality using the Shapiro Wilks test. If the data are found to be normally distributed, central tendency will be expressed using means and dispersion using standard deviation. If the data prove not to be Gaussian, and cannot easily be transformed, they will be summarized using medians, interquartile ranges and ranges. Mean (or median) differences and the standard deviation of the differences will be used to inform sample size calculations for a definitive trial. Confidence intervals will be derived wherever possible. Categorical data will be summarized as proportions and percentages as appropriate with associated confidence intervals. No attempt will be made at this stage to make formal comparisons of outcome measures – this will be done in the eventual definitive study. Summaries of secondary outcome measures will also be produced in a similar manner to the above.

All data management will adhere to GDPR compliance. Statisticians will be blinded to allocation arms.

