19.6 Protocol Compliance

Any deviations from the planned protocol will be documented and reported to the Chief Investigator and Sponsor immediately.

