- h. Discard sutures as per local policy and record the intervention in the medical notes
- i. Dispose any sharps and used instruments safely according to trust policy

If there have been any early post-operative complications, such as dehiscence, infection or poor wound healing, please could you contact the study organisers on the details below.

[name] (CI), [name] (PI), [name] (PI)
Dermatology Department
Heavitree Hospital
Royal Devon and Exeter NHS Foundation Trust
[name]
[name]
[contact]

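### Patients not treated on the allocated day are removed after their arm is known, so the by-arm summaries describe attenders and adherence can be read only from a count of removals that the available text does not plan

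*Combined protocol and SAP*

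**What the plan says.** Objective 5 in section 14 is "To assess follow-up rates and adherence". Section 12 says of the study: "It will also provide an indication as to the ease of recruitment, patient participation, loss to follow-up, and complication rate". Adherence is not defined, and no denominator is given.

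Section 16.4 sets the order of events. After written consent and excision, the patient and an independent nurse or HCA open the next numbered envelope. An appointment for the allocated day is then made with the GP before the patient goes home. If the practice has no capacity, "an appointment will be booked within the dermatology department on the given day for suture removal". The section then states: "If the patient cannot attend the appointment for suture removal specifically on day 7 or 10, they will be removed from the study".

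A second rule acts at the removal visit. Under section 16.5 and step 5 of the SOP (Appendix 13), patients whose sutures are kept in because of actual or threatened dehiscence leave the study. Step 5 asks the remover to tell the study team.

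On analysis, section 17 says: "The statistical analysis for the feasibility study will be descriptive for each group". It mentions neither adherence nor removals. The only timing item on the data collection form (Appendix 8) is the usual recommended interval for the case.

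**The concern.** Both rules act after allocation is known, and both select on whether sutures came out on the allocated day. Patients known to be off-day leave the dataset, so a group summary no longer describes the group that was randomised. An adherence figure taken from those who remain says little about how many patients can keep to an exact day.

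Adherence is a stated objective, and a planner of the definitive trial would want to know how often the allocated day is achieved in each arm, and why it is missed. The 3-month follow-up rate is affected too, since its natural denominator becomes those who attended for removal. No hypothesis test is planned, so what is at stake is the planning information, not a type I error or power claim.

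**Working it through.** **The plan's own figure.** Section 18.4 takes a problem probability of 0.05 and about 95% certainty of seeing it once: n = ln(1 − 0.95)/ln(1 − 0.05) = 58.4, rounded up to 59; the shortcut 3/p = 3/0.05 = 60. Both reproduce. Section 16.4 prepares 60 envelopes, so 60 is the denominator below. The documents give no adherence or removal rate.

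**Adherence, wider reading of the rule.** Suppose it covers inability known at booking and later missed appointments. With N randomised and R removed:

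- over all randomised: (N − R)/N
- among those retained: (N − R)/(N − R) = 1, whatever R is

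The values of R are assumed. Intervals are exact (Clopper-Pearson) 95%, for the all-randomised proportion only. None is given for the retained set, because a proportion fixed by rule has no sampling uncertainty to describe.

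| R (assumed) | Retained set | All randomised | 95% CI, all randomised |
|---|---|---|---|
| 3 | 57/57 = 100% | 57/60 = 95% | 86.1 to 99.0 |
| 6 | 54/54 = 100% | 54/60 = 90% | 79.5 to 96.2 |
| 12 | 48/48 = 100% | 48/60 = 80% | 67.7 to 89.2 |

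**Adherence, narrower reading.** Suppose the rule covers only inability known at booking. Take 6 off-day patients, of whom (assumed) 3 are removed at booking and 3 miss later but stay in. The retained set shows 54/(60 − 3) = 54/57 = 94.7%, against 54/60 = 90% over all randomised. The figure is no longer fixed by rule, but it still overstates.

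**Follow-up.** With 6 removed and a further 3 of the 54 missing the 3-month visit (assumed), 51 have data: 51/54 = 94% of those retained, 51/60 = 85% of those randomised.

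**Could removals be counted from what is collected?**

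- Envelopes: section 16.4 says "The envelope containing the slip of paper with the randomized trial arm will be re-sealed" and filed by participant number, so the number randomised and the arms are recoverable.
- Section 19.6: "Any deviations from the planned protocol will be documented and reported to the Chief Investigator and Sponsor immediately". This is general and not linked to any summary.
- SOP: step 5 reports sutures kept in, and the closing paragraph asks for early complications. Neither asks for the removal date or for notice of off-day attendance. Step h says "record the intervention in the medical notes", which does not bring the date back to the study.
- GP letter (Appendix 12): asks for no return.
- Data collection form: no field for actual removal date, removal from the study or reason.

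The raw material partly exists. The step that turns it into adherence by arm over all randomised is not planned.

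**The case against.** The strongest reply is that the protocol never proposes to measure adherence among retained patients. Under its rule a removal is a case of non-adherence, so removals over all randomised give the answer, and the envelopes, deviation reports and the step 5 notice supply much of it. This stands: a reader might infer that objective 5 cannot be met at all, and the documents do not support that. It does not supply the missing plan to count, and it leaves the outcome summaries restricted to attenders.

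Second, the rule speaks of patients who cannot attend and comes directly after booking. It may not reach a patient who books and then misses, who would fall under section 19.6 and might stay in. This also stands, so the near-100% statement is conditional.

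Third, section 18.4 puts detecting problems ahead of estimating their frequency, and a removal is a detected problem. That is fair as to precision, but section 17 still plans proportions with confidence intervals.

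Two further inferences are tempting. One is that off-day removals nobody reports would be counted as on-day; no section says how they would be classified. The other is that the arms lose patients unequally; the rule is worded alike for both, so this is possible but not shown.

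Finally, the flow chart, information sheet and consent form were not available and might say more about withdrawals.

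**Conclusion.** The point holds in a limited form, with medium confidence, and should be fixed. Sections 16.4 and 16.5 and the SOP exclude patients after randomisation on adherence itself, so the group summaries and 3-month data describe those treated on the allocated day rather than those randomised. That adherence among those retained is close to 100% by construction depends on the attendance rule covering later missed appointments. Objective 5 can be met only from removals counted over all randomised, and the available text plans neither that count by arm nor a field for the removal date, although section 19.6 and SOP step 5 would bring some cases to light.

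The size cannot be known from the documents. The 95%, 90% and 80% figures show only how the all-randomised rate would move under assumed removals. Because the analysis is descriptive, the consequence is weaker planning information for the definitive trial.

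**What to change.** Replace the removal sentence in section 16.4 with wording such as: *A patient whose sutures are not removed on the allocated day is recorded as a deviation, stays in the study unless consent is withdrawn, attends the standard 3-month visit and is reported in the allocated arm.*

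In section 17, define adherence as removal on the allocated day over all randomised. Report it with reasons by arm, and give an on-day-only summary of outcomes as secondary.

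Keep the actual removal date and the reason on a log held by the independent nurse or HCA, not on the data collection form, because the 3-month assessor is blinded. A short GP return should go to that person and not to the investigators named as SOP contacts, since section 16.4 blinds research team members who gather data. Give the statistician only on-day yes/no by coded arm.

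Reconcile section 16.5 and SOP step 5 with this on one matter only: whether patients whose sutures are kept in are still followed and reported. How they are managed, and the removal day itself, are not part of this point.

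Cost: one log, one return slip and a REC amendment, with matching edits to sections 16.4, 16.5 and 17, the SOP, the GP letter and, if needed, the information sheet. There are no extra visits, since section 16.6 describes the 3-month appointment as standard care. The drawbacks are some chasing of GP returns and a slight dilution of the contrast between arms, which the on-day summary makes visible.

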16.5 Wound Dressing and Post-operative Care

Following wound closure, the wounds will be dressed with steristrips, a sterile film and pad dressing as per protocol after skin surgery. After 48 hours, the patients will be instructed to remove the dressing and then gently cleanse the wound and apply petroleum jelly to it twice daily until suture removal. This advice will be given to all patients independent on which trial arm they have been allocated.

Timing of Suture Removal to Reduce Scarring in Skin Surgery

On the day of suture removal, either at GP or in the dermatology department, sutures will be removed as per our standard operating procedure (SOP), available in the department or emailed to the GP practice performing the suture removal (please see appendices).

If there are any signs of wound dehiscence, or that the wound may dehisce on suture removal, the suture may be kept in, as per advice on our SOP. These patients will be withdrawn from the study.

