16.6 Data Collection at 3 Month Follow Up

Patients will be booked in for a 3 month follow-up appointment, as per their standard care pathway. Data collection at 3 month follow up will include completing a patient and observer scar assessment scale (POSAS) with regards to overall scar cosmesis, and also a visual analogue scale (VAS) in relation to suture marks specifically. We have chosen these tools as they are validated, well known scales to characterise scars subjectively and objectively [10].

The patient will be asked about any post-operative complications that were not detected at suture removal including wound infection, dehiscence, and significant post-operative bleeding (defined as bleeding requiring assessment by a healthcare professional). Assessment will be carried out by a member of the research team who will be blinded to trial allocation.

Photographs of the scar will be taken at the follow-up visit using the departmental camera to allow review of scar assessment at a later date if required. This will be directly uploaded onto their electronic patient record in line with Trust policy. Patients will be verbally consented for this at time of follow up, as per usual practice.

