19. ETHICAL AND REGULATORY COMPLIANCE

19.1 Patient Safety and Serious Adverse Events

A serious adverse event (SAE) is any untoward medical occurrence that:

- Results in death;
- Is life-threatening;
- Requires inpatient hospitalization or prolongation of existing hospitalization;
- Results in persistent or significant disability/incapacity;
- Consists of a congenital anomaly or birth defect.

Adverse events (AE) that may occur and for which patients will be consented include:

- Bleeding
- Infection
- Scarring
- Wound dehiscence
- Pain

We do not anticipate there being any increase in adverse events in either arm. The aim of the study is to assess whether early suture removal reduces scarring. It may become apparent that scarring is

Timing of Suture Removal to Reduce Scarring in Skin Surgery

less in the early suture removal arm. We will record the incidence of adverse events in both treatment arms to ensure that patients are not experiencing a greater number of adverse events in either treatment group

This is a pragmatic trial: the nature of the study means that it involves routine clinical practice. There should be no additional risk to patients beyond routine care. With good participant information and subsequent post-trial engagement, we would hope to recruit rapidly to the trial.

All AE's and SAE's will be reported to R&D within 24hrs of the investigator being made aware of the event. An SAE occurring to a participant will be reported to the REC that gave a favourable opinion of the study where the event was related or unexpected. This will be reported within 15 working days.

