22.13 Appendix 13 – Standard Operating Procedure (SOP) for Suture Removal

Standard Operating Procedure (SOP) for Suture Removal

Aim:

The nurse or healthcare assistant is able to assess the wound post operatively, remove the superficial sutures appropriately and recommend simple post-operative wound care

[figure not shown]
Procedure:

1. Confirm the patients identity and gain consent for removal of sutures
2. Wash hands and prepare procedure trolley surface aseptically with correct equipment:
 - a. Disposable Fine tipped non toothed forceps
 - b. Dressing pack – containing sterile gloves and gauze
 - c. Disposable sharp surgical scissors
 - d. Sterile normal saline if required
3. Wash hands and use non-sterile gloves to remove current dressing (if any)
4. The wound should specifically be checked for signs of dehiscence, infection or poor wound healing. If this is the case, medical advice should be sought
5. If the wound shows signs that it may dehisce if sutures are removed at the time, then consider keeping sutures in for removal at a later date at the discretion of the healthcare professional. These patients will be excluded from the study. If this is the case, it is important that you let the study team know by contacting us on the below details.
6. Removal of simple percutaneous interrupted sutures:
 - a. Wash hands and don sterile gloves
 - b. Gently grasp the knot of a suture with forceps and raise it slightly
 - c. Place the tip of the suture scissors directly under the knot or on the side close to the skin
 - d. Gently cut the suture and pull it out gently across the wound with the forceps
 - i. Remove the suture across the wound to minimise any exposed suture passing through the skin and wound during the removal, this can lead to infection. Cutting the correct part of the suture (part directly under the knot on the side closest to the skin), will bypass this from happening
 - e. Place steri-strips on the sites that sutures have been removed. These are applied in opposite directions with a small amount of tension to take tension away from the wound. Educate patient to let the steri-strips fall off naturally (usually 1-2 days). No further treatment to the wound should be required.

Timing of Suture Removal to Reduce Scarring in Skin Surgery

- f. Continue to remove sutures until all sutures have been removed
- g. The application of a suitable wound dressing can be applied at the healthcare professionals discretion

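### Two rules remove patients after randomisation, one of them on wound state; no 3-month study assessment is provided for these patients and their place in the reported rates is not stated.

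*Combined protocol and SAP*

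**What the plan says.** Randomisation follows surgery: sections 16.2 and 16.4 have the patient open the envelope after the excision and before suture removal is booked. Two rules then take patients out.

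- **Wound state.** For signs of dehiscence, or a wound that may open on removal, section 16.5 states "the suture may be kept in, as per advice on our SOP. These patients will be withdrawn from the study". Step 5 of the suture-removal SOP (Appendix 13) repeats this for threatened dehiscence: "These patients will be excluded from the study".
- **Exact day.** Section 16.4: "If the patient cannot attend the appointment for suture removal specifically on day 7 or 10, they will be removed from the study".

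Section 14 lists wound dehiscence (objective 2d) and follow-up rates and adherence (objective 5) among the things to be measured. Objective 1 uses suture marks to size the RCT.

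On capture and analysis:

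- Section 19.1 lists dehiscence as an adverse event and says "We will record the incidence of adverse events in both treatment arms".
- SOP step 5 asks the remover to tell the team when sutures are kept in. The SOP's closing note asks for contact "If there have been any early post-operative complications, such as dehiscence, infection or poor wound healing".
- Section 19.6 requires deviations to be documented and reported.
- Section 16.6, on the 3-month visit: "The patient will be asked about any post-operative complications that were not detected at suture removal".
- The data collection form (Appendix 8) has a time-of-surgery part and a 3-month part, with no entry for the suture-removal visit.
- Section 17: "Categorical data will be summarized as proportions and percentages as appropriate with associated confidence intervals". It names no analysis set, no denominator and no handling of removed patients.

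**The concern.** Both rules act on events that follow allocation, so the patients left in each arm need not be comparable. The wound-state rule is applied at day 7 in one arm and day 10 in the other, so the number and kind of patients removed may differ by arm because of the allocation itself. Wound healing may also be related to scar appearance, so those removed may differ from those kept on suture marks, POSAS and VAS.

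The exact-day rule takes out patients whose removal was not on the allocated day, which is part of what objective 5 sets out to measure.

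At stake are the numbers this feasibility study exists to supply: the suture-mark proportion that sizes the RCT, the scar scores, and the dehiscence and adherence rates used to judge whether the RCT is workable. With no stated denominator, the last two could be reported among all randomised patients or only among those who stayed, with different answers.

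**Working it through.** **1. Timing.** The section 16.3 withdrawal (wound edges that cannot be approximated) comes before the envelope is opened, so it is not counted. The rules in 16.4 and 16.5 come after it. SOP step 5 is the advice that 16.5 refers to, so there are two rules.

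**2. The plan's own figure.** Section 18.4: problem probability p = 0.05, about 95% certainty of seeing it at least once.
- n = ln(0.05)/ln(0.95) = 58.40, rounded up to 59, as stated; 3/p = 60.
- Chance of at least one, 1 − 0.95^n: 95.2% at n = 59 and 95.4% at n = 60.
- If 5%, 10% or 20% of 60 are removed (assumed): 94.6% (n = 57), 93.7% (n = 54), 91.5% (n = 48).

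The stated basis for the sample size is therefore little affected.

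**3. Suture marks.** Take an arm of 30 with k removed and x of 30 − k marked (counts assumed). The all-randomised proportion lies between x/30 and (x + k)/30, a width of k/30.
- k = 1: 1/30 = 3.3 points.
- k = 3: 3/30 = 10 points. With x = 8, the observed 8/27 = 29.6% could be 8/30 = 26.7% to 11/30 = 36.7%.
- k = 6: 6/30 = 20 points.

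**4. What this does to RCT planning.** Assumed: two-sided 5%, 80% power, 15/30 = 50% marked at 10 days with nobody removed there, all removals in the 7-day arm. Per-arm size, with p̄ the mean of p₁ and p₂:

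n = [1.96·√(2p̄(1−p̄)) + 0.842·√(p₁(1−p₁) + p₂(1−p₂))]² / (p₁ − p₂)²

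| Removed | 7-day proportion | n per arm |
|---|---|---|
| k = 3, as observed | 8/27 | 90 |
| k = 3, none of the three marked | 8/30 | 67 |
| k = 3, all three marked | 11/30 | 216 |
| k = 1, as observed | 8/29 | 74 |
| k = 1, not marked | 8/30 | 67 |
| k = 1, marked | 9/30 | 93 |

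**5. Sampling error for comparison.** The Wilson 95% interval for 8/27 is 15.9% to 48.5%, about 33 points wide against 10 for k = 3. Put against 50% in the same formula, its ends give about 29 and 17,000 per arm. Sampling error dominates, but the interval does not reveal or allow for the selection.

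**6. Overt versus threatened dehiscence.** Section 16.5 covers both and withdraws the patient. SOP step 4 covers signs of dehiscence, infection or poor healing and says "If this is the case, medical advice should be sought", with no exclusion. SOP step 5 covers threatened dehiscence and excludes. The documents do not settle what happens to a patient with overt dehiscence, or to one whose sutures are removed despite signs of it.

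**The case against.** The strongest reply is that much of this is already handled. Dehiscence is a listed adverse event recorded in both arms, removers are asked to report it and to report retained sutures, deviations are documented, and the form's dehiscence field carries no time limit. The 3-month appointment is standard care, so withdrawn patients may still be seen. The study is descriptive, and sampling error at 30 per arm far exceeds the effect of a few removals.

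Most of that stands, and it rules out several stronger readings:

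- A reader might infer that early dehiscences vanish. They can reach the team by the routes above; what is unstated is whether they enter the section 17 rates.
- A reader might infer that the 3-month data are certainly lost. No section says that collection stops. The supportable statement is that study assessment after removal is not provided for. The flow chart and patient information sheet were not available to check.
- A reader might infer that the plan will report no dehiscence and full adherence among completers. That needs a completer denominator, which the plan does not state; the number removed could itself be reported under objective 5. Threatened dehiscence without opening is also not objective 2d.
- The exact-day rule follows directly on the booking text, so it may largely concern patients who cannot be booked for that day.

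The reply does not supply a removal-visit entry, an analysis set, or 3-month suture-mark and scar data for patients taken out after allocation. A descriptive proportion still needs a stated denominator.

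**Conclusion.** The concern holds in this form: two post-randomisation removal rules, one tied to wound state judged on different days by arm and one tied to adherence, with no provision for 3-month study assessment of those removed and no statement of where they count. Followed as written, the suture-mark and scar estimates come from patients selected after randomisation. The direction of bias is unknown.

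The size depends on removal counts that the documents do not give: 3.3 points of uncertainty in an arm's suture-mark proportion per patient removed of 30, on top of a larger sampling error. The RCT sizes shown rest on assumed proportions, power and one-sided removals, and are illustrations only. No hypothesis test is harmed, because none is planned.

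A reader might also add that 60 envelopes for 60 analysable cases leaves no slack. That is a separate question of allowance for attrition from any cause, and it adds nothing to this point.

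This should be fixed before recruitment, since 3-month assessments not made cannot be recovered later. Confidence is high that the rules exist and that the analysis set is unstated; it is lower for the size of the consequence.

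**What to change.** 1. In sections 16.4 and 16.5 and SOP step 5, replace removal, withdrawal or exclusion from the study with: *recorded as a deviation from the allocated removal time; the patient stays in 3-month follow-up where consent continues*.
2. Add a short removal-visit entry on a sheet kept from the blinded assessor: date removed, overt dehiscence (yes/no), sutures retained (yes/no).
3. In section 17, state that suture marks, overt dehiscence, retained sutures (separately) and adherence are reported by randomised arm over all randomised patients, with the number missing at 3 months. A per-protocol summary can be secondary.
4. Reconcile section 16.5 with SOP steps 4 and 5 on overt versus threatened dehiscence. The clinical discretion to keep sutures in is unchanged.

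**Cost.** Wording in three protocol sections and the SOP, plus one short sheet. No extra visit is needed, because section 16.6 places the 3-month appointment on the standard care pathway. The change may need an ethics committee amendment (sections 19.4 and 19.5) and a check of the patient information and consent text. The downside is that each arm will include a few patients whose sutures were not removed on the allocated day.
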